I will conduct the trial in accordance with the clinical investigation plan, Good Clinical Practice guidelines, ISO 14155:2011 (Clinical Investigation of Medical Devices for Human Subjects - Good Clinical Practice), as well as local regulations. I also accept respective revisions to the clinical investigation plan approved by authorized personnel of the Sponsor and by regulatory authorities.

Institution:

[name] [name]

Principal Investigator (Printed name)

Principal Investigator (Signature)

22/2/18

Date

PROTOCOL SUMMARY

TITLE	Clinical Evaluation of the Safety and Performance of Fractional RF for the Treatment of Surgical Scars Following Breast Augmentation, Abdominoplasty or Face Lift
SUMMARY	Split-body/face evaluator-blind study of the safety and performance of fractional RF for the treatment of surgical scars following breast augmentation, abdominoplasty or face lift. The study will enroll up to 50 female subjects requesting treatment of surgical scars following breast augmentation or abdominoplasty and up to 25 male and female subjects requesting treatment of surgical scars following face lift surgery. Subjects will receive a total of three treatments of their surgical scars at one-month intervals on one side of the body or facial incision only. Subjects will be followed up at one, two, three and ten months after their last treatment. Analysis will be performed on all subjects who receive at least one treatment. Outcomes will be compared to the non-treated side.
OBJECTIVES	The objective of this clinical study is to evaluate the safety and performance of fractional RF for the treatment of surgical scars following breast augmentation, abdominoplasty or face lift.

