7.3.2 ENROLLMENT/BASELINE

Enrollment/Baseline Visit (Visit 2, Day 0)

Once a subject has been confirmed that they continue to meet inclusion/exclusion criteria, they will receive a unique identifying number that will be composed of a two-digit site number and a two-digit subject number in sequence. This unique identifier will be used throughout the entire study and will be entered in the subject's case report form (CRF). The investigator will confirm that the subject still meets the inclusion/exclusion criteria. Vital signs and demographics will be collected and a physical exam will be performed. The subject will complete the POSAS.

Photography

Photographs will be taken prior to first treatment and throughout the study according to specified time points detailed in the Schedule of Events Table (section 7.3.7), utilizing standard scientific equipment. Two sets of photographs will be required, one set for the treated side of the body/face and a second set for the untreated side of the body/face.

The photos should be taken in a private room or area of the clinic under controlled conditions, including the distance, angle, background and lighting in order to achieve high-quality sets of photographs. Direct illumination will not be used. The subject should be placed in the same position each time. As each photograph is taken, it should be viewed to ensure that it is in focus and is similar to its baseline counterpart in all technical aspects, including lighting, distance and angle.

For consistency purposes, the same person should ideally take all study photographs, especially per subject. The digital files should follow a consistent standard naming scheme.

Treatment

Subjects will receive treatment as described in section 7.3.1. Only one side of the body/face will be treated. The same side will be treated for the duration of the study. Only half of a scar will be treated

and remaining half will serve as the control. Following treatment, the investigator will examine the treated area and report immediate and short term response. Subjects will complete the 10 cm discomfort/pain VAS immediately after treatment. A new disposal tip will be used for each patient treatment.

Treatment procedure should include positioning of the patient in a manner that enables comfortable access to the treated anatomical site.

Assessment

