
Subjects will return to the clinic one month after the last assessment. Adverse events, vital signs and any changes to concomitant medications will be recorded.

Photographs of the treated area will be taken as described in section 7.3.1. Subjects will be discharged from the clinic and will be instructed to return for the Month 5 assessment.

Visit 10, Month 5 (\pm 7 days)

Subjects will return to the clinic one month after the last assessment. Adverse events, vital signs and any changes to concomitant medications will be recorded. Subjects will complete a 5-point Likert satisfaction questionnaire and the POSAS.

Photographs of the treated area will be taken as described in section 7.3.1. Subjects will be discharged from the clinic and will be instructed to return for the final Month 12 assessment.

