7.3.7 SCHEDULE OF EVENTS TABLE

Procedures	Screening/Baseline (Visit 1, Day -1)	Enrollment/Treatment (Visit 2, Day 0)	Follow-up (Visit 3, Day 0+2 days)	Treatment & Follow-up (Visit 4, Month 1 (± 7 days))	Follow-up (Visit 5, Month 1+2 days)	Treatment & Follow-up (Visit 6, Month 2 (± 7 days))	Follow-up (Visit 7, Month 2+2 days)	Follow-up (Visit 8, Month 3 (± 7 days))	Follow-up (Visit 9, Month 4 (± 7 days))	Follow-up (Visit 10, Month 5 (± 7 days))	Final Study Visit (Visit 11, Month 12 (± 14 days))
Informed consent	X										
Inclusion/exclusion criteria	X	X									
Demographics	X										
Medical history	X										
Physical exam	X										
Vital signs		X	X	X	X	X	X	X	X	X	X
Urine pregnancy test ^a	X										
Test Spot	X										
Photographs		X						X	X	X	X
Administer Treatment		X		X		X					
Discomfort/Pain VAS	X		X		X						
PI immediate & short-term response	X		X		X						
Blinded reviewer GAIS		X						X	X	X	X
Blinded reviewer MSS	X							X	X	X	X
Blinded reviewer POSAS	X									X	X
Subject POSAS	X									X	X
Subject satisfaction questionnaire										X	X
Concomitant medication	X	X	X	X	X	X	X	X	X	X	X
Adverse event evaluation		X	X	X	X	X	X	X	X	X	X

Procedures	Screening/Baseline (Visit 1, Day -1)	Enrollment/Treatment (Visit 2, Day 0)	Follow-up (Visit 3, Day 0+2 days)	Treatment & Follow-up (Visit 4, Month 1 (± 7 days))	Follow-up (Visit 5, Month 1+2 days)	Treatment & Follow-up (Visit 6, Month 2 (± 7 days))	Follow-up (Visit 7, Month 2+2 days)	Follow-up (Visit 8, Month 3 (± 7 days))	Follow-up (Visit 9, Month 4 (± 7 days))	Follow-up (Visit 10, Month 5 (± 7 days))	Final Study Visit (Visit 11, Month 12 (± 14 days))
^a For women of child-bearing potential.											

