 - **Null Hypothesis ($H_0: \mu_d = \mu_{post} - \mu_{pre} = 0$)** – There is no improvement of surgical scars at 3 and 10 months post-treatment review compared to baseline.
Alternative Hypothesis ($H_a: \mu_d = \mu_{post} - \mu_{pre} \neq 0$) – There is improvement of surgical scars at 3 and 10 months post-treatment review compared to baseline. The improvement of surgical scars will be defined using Patient and Observer Scar Assessment Scale (POSAS) scores evaluated by the subject.
 - **Null Hypothesis ($H_0: \mu_d = \mu_{post} - \mu_{pre} = 0$)** – There is no satisfaction with treatment as documented on a 5-point Likert scale at 3 and 10 months compared to baseline.
Alternative Hypothesis ($H_a: \mu_d = \mu_{post} - \mu_{pre} \neq 0$) – There is satisfaction with treatment as documented on a 5-point Likert scale at 3 and 10 months compared to baseline. The satisfaction with treatment will be defined by 5-point Likert scale at 3 and 10 months compared to baseline as assessed by the subjects.
- Safety Endpoint:
 - **Null Hypothesis ($H_0: \mu_d = \mu_{post} - \mu_{pre} = 0$)** – There is no difference in subjects' 10 cm discomfort/pain VAS score experienced after at Visit 6 treatment and that of baseline treatment (Visit 2).
Alternative Hypothesis ($H_a: \mu_d = \mu_{post} - \mu_{pre} \neq 0$) – There is a difference in subjects' 10 cm discomfort/pain VAS score experienced after at Visit 6 treatment and that of baseline treatment (Visit 2). Expected mean difference is maximum VAS score ≤ 1 .

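### The plan does not say which part of the scar the subject POSAS rates and provides no subject rating of the untreated part, so as written this secondary endpoint has no control value

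*Combined protocol and SAP*

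**What the plan says.** Subject-rated POSAS at 3 and 10 months after treatment is a named secondary endpoint (Protocol Summary; Section 4.2.2). The instructions for collecting it are short:

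- Baseline (Section 7.3.2): "The subject will complete the POSAS".
- Visit 10, Month 5 (Section 7.3.3), and in the same words Visit 11, Month 12 (Section 7.3.4): "Subjects will complete a 5-point Likert satisfaction questionnaire and the POSAS".
- Schedule of events (Section 7.3.7): a single row, "Subject POSAS", with one mark per time point and no side.

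Section 7.3.2 also states "Only half of a scar will be treated" and makes the remaining half the control. For photographs it does name the side: "Two sets of photographs will be required, one set for the treated side of the body/face and a second set" for the untreated side.

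The Protocol Summary gives the comparator for the trial: "Outcomes will be compared to the non-treated side". For this endpoint, however, Section 10.2 tests post minus pre equal to zero and adds "The improvement of surgical scars will be defined using Patient and Observer Scar Assessment Scale (POSAS) scores evaluated by the subject". Section 10.4.3 summarises POSAS as the difference from baseline. Neither contains a side term.

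**The concern.** A split-scar design earns its value by rating both parts. Here the person filling in the form is not told whether to rate the treated part, the untreated part or the whole scar, and nothing asks for the untreated part separately.

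Entry is allowed from four weeks after surgery (Section 5.2) and follow-up runs to Month 12, so scar change without treatment is plausible. A pre-post patient rating would credit that change to the device.

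The gap cannot be closed afterwards. Reviewer scales are scored from photographs that Section 7.3.2 requires for both sides, so they could be re-scored by side. The subject's form is itself a source document (Section 11), and an untreated-part rating not taken at the visit is lost. The other subject-reported endpoints are satisfaction with the treatment and the pain VAS, and neither rates the scar.

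**Working it through.** **Plan's own figure.** The documents give no effect, SD or sample size for POSAS. The only sample-size calculation is for the GAIS pre-post change (Section 10.5): mean difference 1.0, SD of differences 1.0, two-sided alpha 0.05, power 0.90.

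n = ((z for alpha + z for power) × SD / difference)² = ((1.96 + 1.2816) × 1.0 / 1.0)² = 10.51, rounded up to 11. With the plan's dropout allowance, 11 × 1.3 = 14.3, rounded up to 15. Both figures reproduce. The 0.84 printed beside 90% power would give (1.96 + 0.84)² = 7.84, so it is not the value used.

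**What each way of rating records.** Let T be the device effect and c the natural scar change, with improvement positive. The treated half changes by d = T + c and the untreated half by c.

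| What the subject rates | Recorded change | Can T be separated from c? |
|---|---|---|
| Treated half only | T + c | No |
| Whole scar, as the average of two halves (assumed) | (d + c)/2 = 0.5T + c | No, and T is halved |
| Both halves, on separate forms | (T + c) − c = T | Yes, apart from expectation bias |

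Two examples for the whole-scar case:

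- With d = 2 and c = 0, the form shows (2 + 0)/2 = 1, against a true between-half difference of 2.
- With d = c = 2, there is no device effect, yet the form shows (2 + 2)/2 = 2.

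**Illustration of size.** The GAIS standardised effect of 1.0 is borrowed because POSAS has none. Power comes from the noncentral t distribution for a paired test of change from baseline, with T and c in SD units.

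| T | c | What is rated | Recorded change | P(significant), n = 11 | n = 15 |
|---|---|---|---|---|---|
| 1 | 0 | treated half only | 1.0 | 0.85 | 0.95 |
| 1 | 0 | whole scar | 0.5 | 0.32 | 0.44 |
| 0 | 0.25 | either | 0.25 | 0.12 | 0.15 |
| 0 | 0.5 | either | 0.5 | 0.32 | 0.44 |
| 0 | 1.0 | either | 1.0 | 0.85 | 0.95 |

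Rows two and four are identical. On a whole-scar rating, a full device effect with no natural change looks exactly like no device effect with 0.5 SD of natural change. More subjects do not help: at n = 25 both probabilities are 0.67, and at n = 50 both are 0.93. By the normal approximation, 90% power for a recorded change of 0.5 needs 10.507/0.5² = 42.03, that is 43 subjects instead of 11.

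**With both parts rated.** If each part's change has SD 1 and the between-part correlation is ρ, the difference in change has SD √(2(1 − ρ)). Then n = 10.507 × 2(1 − ρ), which gives 22, 16, 11 and 5 for ρ = 0, 0.25, 0.5 and 0.8. The documents give no ρ, so this is a range. Natural change common to both parts cancels.

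**The case against.** Several stronger readings are tempting, and the documents do not support them.

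- **Exactly one form is completed per visit.** The documents never count POSAS forms and do not include the CRF. The single schedule row proves little, because photographs also have one row yet Section 7.3.2 requires two sets.
- **The rating mixes treated and untreated skin.** That follows only if the subject rates the whole scar. A subject who thinks only of the treated part mixes nothing, but still supplies no control value.
- **An untreated rating cannot exist in any analysis.** The general statement in the Protocol Summary suggests that a comparison was intended. The procedures and statistics do not say how the subject form would supply it, so this is under-specification with consequences. It is not proof that the data will be absent.
- **Every subject has one scar divided in two.** Section 7.3.2 refers both to treating one side of the body or face and to treating half of a scar. For separate scars on each side these may differ, and the averaging rule need not apply.

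Two further objections are fair. The missing side contrast is not peculiar to this endpoint, since every performance hypothesis in Section 10.2 is post minus pre; only the collection gap is specific to the subject POSAS. And only the independent reviewers are blinded (Section 10.6.2), so a self-rated side contrast is open to expectation bias.

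What stands is that no section provides for a subject rating of the untreated part. If the CRF does hold two forms, the visit text, schedule and analysis still need to say so.

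**Conclusion.** The concern holds in this form: the area rated by the subject POSAS is undefined, no control rating is provided for, and the planned test is change from baseline alone. Followed as written, the endpoint cannot distinguish a device effect from natural scar change, whichever part the subject has in mind. That conclusion needs no numerical assumption.

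The dilution is conditional. It is about half if the whole scar is rated and the rating averages two equal halves. The power figures also borrow the GAIS effect of 1.0 SD, so they illustrate the mechanism and do not estimate the harm to POSAS.

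This is a secondary endpoint and the primary endpoints are not affected by this point. It should still be corrected, because the missing rating cannot be recovered after the visit.

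**What to change.** - At Visit 2 before treatment, Visit 10 and Visit 11, have the subject complete two labelled POSAS patient forms, one for the treated and one for the untreated half or side. Add both to the visit text, the schedule and the CRF.
- In Sections 10.2 and 10.4.3, make the reported contrast for this endpoint the within-subject treated-minus-untreated difference in change from baseline.
- Reconcile the two descriptions of the treated area in Section 7.3.2, so that the two areas to be rated are defined for each type of scar.
- State that subjects know which part was treated and that the contrast is to be interpreted with that limit.

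The cost is one more short questionnaire at three visits that already take place, a few minutes per subject, and wording changes. The remaining weakness is expectation bias, which two forms do not remove.

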7.3.4 FINAL STUDY VISIT

Visit 11, Month 12 (\pm 14 days)

Subjects will return to the clinic seven months after the last assessment. Adverse events, vital signs and any changes to concomitant medications will be recorded. Subjects will complete a 5-point Likert satisfaction questionnaire and the POSAS.

Photographs of the treated area will be taken as described in section 7.3.1. The photographs will be sent to the blinded independent reviewer for assessment (GAIS, MSS and POSAS). The termination form will be completed and subjects will be discharged from the clinic and terminated from the study. The PI will

record all reportable events with start dates occurring any time after informed consent is obtained until 7 (for non-serious AEs) or 30 days (for SAEs) after the last day of study participation.

After the study is completed, subjects will be offered treatment on their untreated side (body/face).

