4.2.2 SECONDARY PERFORMANCE ENDPOINTS

- Improvement in appearance of surgical scars at 1 and 2 months post-treatment as evaluated by independent blinded reviewer using the General Aesthetic Improvement Scale (GAIS) and Manchester Scar Scale (MSS).
- Assessment of surgical scars at 3 and 10 months post-treatment as evaluated by independent blinded reviewer using the Patient and Observer Scar Assessment Scale (POSAS).
- Assessment of surgical scars at 3 and 10 months post-treatment as evaluated by the subject using the Patient and Observer Scar Assessment Scale (POSAS).
- Subjects' assessment of satisfaction (5-point Likert Scale) with the treatment at 3 and 10 months post-treatment.

Safety endpoints:

- Subject's assessment of discomfort and pain after treatment as measured by a 10 cm visual analog scale (VAS).
- Subjects experiencing a treatment-related adverse event (AE) by 10 months post-treatment.

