5.4 STRATEGIES FOR RECRUITMENT AND RETENTION

Up to 50 female subjects with surgical scars due to breast augmentation or abdominoplasty and 25 male and female subjects with surgical scars due to face lift surgery will be enrolled at the single investigative site. It is anticipated that it will take up to fifteen months to complete the study. A qualified dermatologist or plastic surgeon will be the recruited to participate as an investigator. Subjects will be primarily be recruited primarily from the investigator's practice. Any advertising campaigns and materials will be reviewed and approved by an Ethics Committee or Institutional Review Board (EC or IRB) before implementation. Due to the long duration of the study, subjects will be contacted by the investigative site on a regular basis in order to enhance retention.

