7.3.3 FOLLOW-UP

Visit 3, Day 0+2 days

Subjects will be examined 2-3 days after treatment for the occurrence of adverse events. Vital signs and any changes in concomitant medication will be recorded. Subjects will be discharged from the clinic and will be instructed to return for the Month 1 assessment and treatment.

Visit 4, Month 1 (\pm 7 days)

Subjects will return to the clinic one month after the first treatment. Adverse events, vital signs and any changes to concomitant medications will be recorded.

Subjects will receive treatment as described in section 7.3.1. Following treatment, the investigator will examine the treated area and report immediate and short term response. Subjects will complete the 10 cm discomfort/pain VAS immediately after treatment.

Subjects will be discharged from the clinic and will be instructed to return in 2-3 days in order to be examined for adverse events.

Visit 5, Month 1+2 days

Subjects will be examined 2-3 days after treatment for the occurrence of adverse events. Vital signs and any changes in concomitant medication will be recorded. Subjects will be discharged from the clinic and will be instructed to return for the Month 2 assessment and treatment.

Visit 6, Month 2 (\pm 7 days)

Subjects will return to the clinic one month after the second treatment. Adverse events, vital signs and any changes to concomitant medications will be recorded.

Subjects will receive treatment as described in section 7.3.1. Following treatment, the investigator will examine the treated area and report immediate and short term response. Subjects will complete the 10 cm discomfort/pain VAS immediately after treatment.

Subjects will be discharged from the clinic and will be instructed to return in 2-3 days in order to be examined for adverse events.

Visit 7, Month 2+2 days

Subjects will be examined 2-3 days after treatment for the occurrence of adverse events. Vital signs and any changes in concomitant medication will be recorded. Subjects will be discharged from the clinic and will be instructed to return for the Month 3 assessment.

Visit 8, Month 3 (\pm 7 days)

Subjects will return to the clinic one month after the third treatment. Adverse events, vital signs and any changes to concomitant medications will be recorded.

Photographs of the treated area will be taken as described in section 7.3.1. Subjects will be discharged from the clinic and will be instructed to return for the Month 4 assessment.

Visit 9, Month 4 (\pm 7 days)

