8.3 TIME PERIOD AND FREQUENCY FOR EVENT ASSESSMENT AND FOLLOW-UP

The occurrence of an AE or SAE may come to the attention of study personnel during study visits and interviews of a study participant presenting for medical care, or upon review by a study monitor. All AEs including local and systemic reactions not meeting the criteria for SAEs will be captured on the appropriate CRF. Information to be collected includes event description, time of onset, clinician's assessment of severity, relationship to investigational device and study procedures (assessed only by those with the training and authority to make a diagnosis), and time of resolution/stabilization of the event. All AEs occurring while on study must be documented appropriately regardless of relationship. All AEs will be followed to adequate resolution.

Any medical condition that is present at the time that the participant is screened will be considered as baseline and not reported as an AE. However, if the study participant's condition deteriorates at any time during the study, it will be recorded as an AE.

Changes in the severity of an AE will be documented to allow an assessment of the duration of the event at each level of severity to be performed. AEs characterized as intermittent require documentation of onset and duration of each episode.

The PI will record all adverse events with start dates occurring any time after informed consent is obtained. At each study visit, the investigator will inquire study subjects about the occurrence of AE/SAEs since the last visit. All adverse events need to be followed until resolution or until study end, whichever occurs first.

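### No active adverse-event enquiry is scheduled between Month 5 and Month 12, so short-lived late events, their dates and the treatments used then depend on passive reporting or on recall of up to about seven months

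*Combined protocol and SAP*

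**What the plan says.** One of the two safety endpoints in section 4.2.2 is "Subjects experiencing a treatment-related adverse event (AE) by 10 months post-treatment". Section 8.3 sets how events are elicited: "At each study visit, the investigator will inquire study subjects about the occurrence of AE/SAEs since the last visit".

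The visits after the last treatment are laid out in sections 7.3.3 and 7.3.4. For Visit 8 (Month 3), "Subjects will return to the clinic one month after the third treatment". At Visit 10 (Month 5) subjects "will be instructed to return for the final Month 12 assessment". For Visit 11, "Subjects will return to the clinic seven months after the last assessment". The schedule of events (7.3.7) marks AE evaluation at Visits 2 to 11 and lists no visit or call between Visit 10 and Visit 11.

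Section 5.4, citing the length of the study, adds that "subjects will be contacted by the investigative site on a regular basis in order to enhance retention". It gives neither the timing nor the content of these contacts.

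Other routes by which an event can reach the record are an unscheduled visit (7.3.6), a subject's complaint (7.8), a subject presenting for medical care or a monitor's review (8.3), and spontaneous reports (8.1, 10.4.4).

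**The concern.** The sponsor chose a safety horizon of 10 months after the last treatment, but most of that horizon is covered by a single look back at its end. Several of the plan's own data requirements are hard to meet from memory over that span. Section 8.3 asks for onset and resolution times, for changes in severity so that duration at each level can be assessed, and for each episode of an intermittent event. Section 7.5 asks for prescription, over-the-counter and herbal products.

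Loss to follow-up works in the same direction. Section 10.3 keeps a subject in the safety set after one treatment and one valid post-baseline evaluation. Section 10.4.4 reports the number and percentage of subjects with an AE and gives no rule for incomplete AE follow-up; imputation is mentioned only for performance endpoints (10.4.2, 10.4.3). A subject lost after Month 5 can therefore stay in the denominator with nothing recorded for the interval.

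The 24-hour SAE report in section 8.4.2 also depends, for those seven months, on the event reaching the site without being asked about.

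**Working it through.** **Inputs.** Third treatment one month before Month 3 (7.3.3); Visit 10 at Month 5 ± 7 days and Visit 11 at Month 12 ± 14 days (7.3.3, 7.3.4, 7.3.7); AE evaluation at Visits 2 to 11 (7.3.7); maximum enrolment 50 + 25 = 75 (5.1); 30% provision for dropout, withdrawal or loss (10.5). One month is taken as 30.4375 days.

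**1. Reproduce the plan's timing.** Last treatment: 3 − 1 = Month 2. Visit 10 is 5 − 2 = 3 months and Visit 11 is 12 − 2 = 10 months post-treatment, which matches the endpoints. Gap: 12 − 5 = 7 months, as section 7.3.4 states.

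**2. Gap in days.** 7 × 30.4375 = 213. With the windows at opposite extremes: 213 − (7 + 14) = 192, and 213 + (7 + 14) = 234, or 6.3 to 7.7 months. If the 14-day window is counted from the actual date of Visit 10, the range is 213 ± 14 = 199 to 227 days. The conclusion is the same.

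**3. Spacing of the ten AE evaluations.** Taking each post-treatment check at 2 days, the gaps in months are 0.07, 0.93, 0.07, 0.93, 0.07, 0.93, 1, 1 and 7. Nine of the ten evaluations fall by Month 5, none more than about a month after the one before. The last gap is 7/12 = 58% of participation and 7/10 = 70% of the time after the last treatment.

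**4. What depends on passive reporting or recall.**

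| Event | Occurrence | Onset and duration |
|---|---|---|
| Starts by Month 5 | Asked about within about a month | Onset covered; later course exposed if still ongoing |
| Starts after Month 5, visible at Month 12 | Seen at the visit | Onset exposed |
| Starts after Month 5, resolved by Month 12 | Exposed | Exposed |
| Starts after Month 5 in a subject lost after Month 5 | Unknown unless reached | Unknown unless reached |

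Because the endpoint counts subjects, a missed late event changes it only for a subject with no earlier related AE.

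**5. Size, by assumption only.** Let q be the share of subjects whose first related AE falls in the third row, and r the probability that it is reported or recalled. Neither is in the documents. True cases are N × q, recorded cases N × q × r, missed cases N × q × (1 − r). For N = 75, q from 2% to 10% and r from 50% to 90%:
- True cases: 75 × 0.02 = 1.5 to 75 × 0.10 = 7.5.
- Recorded: 1.5 × 0.5 = 0.8 to 7.5 × 0.9 = 6.8.
- Missed: 1.5 × 0.1 = 0.15 to 7.5 × 0.5 = 3.75.

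This shows scale; it is not an estimate.

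**6. Effect of added contacts.** With k evenly spaced contacts the longest nominal look-back is 7/(k + 1) months: 3.5 for one, 2.3 for two, 1.75 for three and 1.0 for six. Contacts at Months 7 and 9 give gaps of 2, 2 and 3 months, so the longest is 3.

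**The case against.** The strongest reply is that little is at risk. The endpoint is cumulative, subjects are examined 2 to 3 days after every treatment, and nine of ten AE evaluations fall by Month 5. A persistent change can be seen at Month 12, in person and on photographs, without anyone having to remember it. Passive routes exist, and section 8.3 requires AEs to be followed up. For subjects who leave, sections 5.5.1, 5.5.2 and 7.3.5 provide for attempts at contact, an exit visit and recording of AEs. This is a post-marketing study of a device judged non-significant risk (2.2), with low potential for serious events (7.4). Sparse late follow-up with a final visit is a legitimate design choice, and the documents contain no contradiction here.

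All of that stands, and it rules out several stronger readings that a reader might infer:
- **That the endpoint as a whole rests on seven-month recall.** Only the exposed entries in the table do.
- **That subjects lost after Month 5 give no information.** They keep their earlier AE data and may still be reached.
- **That the retention contacts exclude an AE question.** Section 5.4 is silent on content; a question is not specified, but it is not ruled out.
- **That 30% are lost in this interval.** Section 10.5 makes that provision for the whole study.
- **That pigment change, scarring and hair loss are late effects.** Sections 2.3.1 and 8.2.3 list them as risks without saying when they appear.

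None of these points supplies an active enquiry in the gap. The exit and early-termination visits depend on the subject's willingness, and the passive routes need the subject to come forward or the event to be in a record that someone checks.

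**Conclusion.** The point holds in a limited form. No active AE enquiry is scheduled for 7 months (192 to 234 days with windows), and capture in that time is passive. Exposed are events that start after Month 5 and resolve before Month 12, the dating of events in that interval, concomitant treatments used then, and the whole interval for subjects who are lost and not reached.

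A reader might go further and conclude that the 10-month AE rate will be understated by a material amount. The documents do not support that: they give no late-event rate, no recall probability and no loss rate for this interval. The direction of any error in the count is towards under-recording; its size is unknown. The verdict assumes that the schedule table is complete and that the retention contacts carry no AE question unless one is written in. It is a worthwhile, inexpensive improvement, not an error that undermines the trial.

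**What to change.** - In sections 5.4 and 8.3, set at least two of the planned retention contacts at stated, roughly even times between Visits 10 and 11. Even spacing falls near Months 7.3 and 9.7 (5 + 7/3 and 5 + 14/3).
- At each, ask one scripted question covering new or changed skin findings on either side, any other AE, and any treatment sought. Asking about both sides alike keeps the treated and untreated sides comparable.
- Record the answers on the AE and concomitant medication CRFs, and add the contacts to the schedule in 7.3.7.

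The cost is a few minutes of site time per contact, plus a short protocol amendment with EC/IRB approval (13.2) and brief site training. Because section 5.4 fixes no frequency, the timing of the contacts is a new commitment even though contact itself is already planned. No clinic visit, treatment, endpoint or sample size changes.
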